**Table 1 Treatment Group Identifiers**

Treatment Group	Descriptor
Mepolizumab 100mg SC every 4 weeks	Mepolizumab 100mg SC

## 8. GENERAL CONSIDERATIONS FOR DATA ANALYSES

Programming will be performed in a HARP environment using SAS Version 9 or a later release.

Summary tables will include N, the number of subjects in the treatment group, and n, the number of subjects with non-missing values.

### 8.1. Multicentre Studies

Centres will be grouped into regions. The following regions are defined:

- USA
- European Union (France, Germany, Poland, Romania, UK)
- Europe Non-EU (Russia, Ukraine)
- South America (Argentina, Chile)
- Rest of World (Australia, Canada, Korea)

The variable CENTREID will be used to identify investigators.

### 8.2. Other Strata and Covariates

A covariate for region as described above will be included in all model-based analyses. Terms for baseline disease severity (as baseline % predicted pre-bronchodilator FEV1), the annualised rate of exacerbations in the interval between the MEA112997 trial and the screening visit of this study (as an ordinal variable: 0.0-<1.0, 1.0-<2.0, 2.0-<3.0, 3.0-<4.0, ≥4, See Section 9.2.3) and time on-treatment (as an offset variable) will also be included when estimating the annualised rate of exacerbations.

If there are insufficient subjects in each region or exacerbation rate category for the statistical procedures to converge satisfactorily, further combining of these covariates will be considered.

### 8.3. Examination of Subgroups

Tabulations of adverse events, immunogenicity and blood eosinophil data will also be reproduced by drug product administered in order to investigate whether there is a differential effect of the two drug products used within the trial (See Section 12 and Section 11.5).

The annualised rate of exacerbations will also be estimated according to blood eosinophil level of  $\geq 150/\mu\text{L}$  or  $< 150/\mu\text{L}$  at baseline within MEA115666.

#### **8.4. Multiple Comparisons and Multiplicity**

Not applicable.

### **9. DATA HANDLING CONVENTIONS**

Details of key definitions and data handling conventions are detailed below as appropriate.

#### **9.1. Withdrawal and Missing Data**

##### **9.1.1. Screening and Enrollment**

A subject is considered a Screen Failure if he/she has been assigned a subject identifier but does not continue in the study beyond Visit 1 (Screening). A subject is considered a Run-in Failure if he/she is not a Screen Failure and entered the run-in period, but was not dosed with mepolizumab.

##### **9.1.2. Missing Data**

The primary reason for withdrawal will be recorded in the electronic case report form (eCRF) and any data collected up until the point of withdrawal will be used in the data analyses. No imputation will be performed if a subject drops out of the study for any reason, or is lost to follow-up, and their response is unknown.

#### **9.2. Derived and Transformed Data**

##### **9.2.1. Definition of Baseline and Change from Baseline**

The baseline values for each assessment will be the Visit 2 pre-dose assessment. If a value is missing at Visit 2 then the value recorded at Visit 1 (Screening) will be used as the baseline.

For ECG, clinical chemistry and haematology assessments not scheduled for collection at Visit 2, the baseline value will be that recorded at Visit 1 (Screening).

Generally change from baseline will be defined as the difference between the value of the endpoint at the time point of interest and the baseline value. However, if stated below, a change from baseline analysis may be performed on the ratio scale and change from baseline will be the ratio: time point of interest value/baseline value.

### 9.2.2. Exacerbations within MEA115666

Exacerbations of asthma will be defined as worsening of asthma which requires use of systemic corticosteroids and/or hospitalisation and/or Emergency Department (ED) visits.

For all subjects, IV or oral steroid (e.g., prednisone) for at least 3 days or a single IM CS dose is required. For subjects on maintenance systemic corticosteroids, at least double the existing maintenance dose for at least 3 days is required.

The on-treatment collection period for exacerbations will be defined as being from Visit 2 until either the date of the data collection cut-off or the date of withdrawal inclusive (but no greater than 4 weeks post last study dose received), See Section 9.3.1. For consistency, exacerbations separated by less than 7 days will be treated as a continuation of the same exacerbation.

It should be noted that exacerbations recorded in the eCRF will not be verified using eDiary data to confirm that the exacerbation was associated with changes in peak flow, rescue medication use, nocturnal awakening due to asthma symptoms requiring rescue medication use or symptoms. However, 96% of exacerbations captured within MEA112997 met the protocol-defined exacerbation criteria, and only in 4% of the cases were the site/PI not able to provide any objective data to justify the use of corticosteroids.

### 9.2.3. Annualised Rate of Exacerbations in the Interval Between Studies

The annualised rate of exacerbations in the gap between the MEA112997 trial and the screening visit of this study will be calculated as:

For those subjects that completed the study:

$$\frac{\text{Total Number of Exacerbations Since the Completion of MEA112997}}{((\text{Date of Screening MEA115666}) - (\text{Visit 16 (Week 52) date}))/365.25}$$

For those subjects that withdrew from the trial early:

$$\frac{\text{Total Number of Exacerbations Since the Completion of MEA112997}}{((\text{Date of Screening MEA115666}) - (\text{Date of withdrawal}))/365.25}$$

This rate will be derived and then categorised as explained in Section 8.2. A value of 365.25 represents the average number of days in a year.

It should be noted that the number of exacerbations reported between the completion of MEA112997 and screening of MEA115666 is self-reported and not subject to verification.

#### 9.2.4. Percent Predicted FEV1

The predicted normal FEV1 is based on the NHANES III equations [Hankinson, 1999] and [Hankinson, 2010]. If a subject is recorded as having Hispanic or Latino ethnicity then the Mexican-American equation will be used (irrespective of race). Otherwise, if a subject is recorded as being African-American/African Heritage race, then the African-American equation will be used, similarly if a subject is recorded as being of Asian race, then the Asian equation will be used. Otherwise the Caucasian equation is used.

#### 9.2.5. 12-Lead ECG

'Maximum post-baseline' QTc(F) and QTc(B) values will be derived as the maximum value recorded at any scheduled or unscheduled visit during the treatment period.

#### 9.2.6. Log Transformed Data

Where log-transformed data are used, then summary statistics for these endpoints will include geometric mean, and a measure of spread (SD or SE) on the natural log scale.

Values of zero will be imputed as 0.005 for that measure prior to the log transformation.

### 9.3. Assessment Windows

Clinic visits are scheduled to take place as specified in the protocol. Measurements outside visit windows will not be excluded from analyses on any population.

If a subject withdraws at a scheduled visit, and these data were scheduled to be collected at that visit, the data will be summarised and analysed (as appropriate) together with data from subjects who did not withdraw.

If a subject withdraws at a scheduled visit at which these data were **not** scheduled to be collected, or if a subject withdraws between scheduled visits, data will be slotted to the next visit.

#### 9.3.1. On-Treatment Exacerbations

In order to model the annualised rate of exacerbations, the reporting period for exacerbations will be as follows:

For subjects remaining in the study:  
(Data collection cut-off date) – (Visit 2 date) + 1.

For early withdrawals:  
(Date of withdrawal) – (Visit 2 date) + 1.

The on-treatment collection period for exacerbations will be defined as being from Visit 2 until either the date of the data collection cut-off or the date of withdrawal inclusive (but no greater than 4 weeks post last study dose received).

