4.5. Withdrawal Criteria

Subjects may be withdrawn from study treatment at anytime by the Investigator if it is considered to be detrimental for them to continue in the study. Reasons for withdrawal can include: an adverse event, lost to follow-up, protocol violation, lack of efficacy, sponsor terminated study, non-compliance, pregnancy, abnormal liver function test, abnormal laboratory results, or for any other reason. Liver chemistry stopping criteria are detailed in Section 6.3.2. In addition, QTc discontinuation criteria are listed below:

- QTc(F)>500 msec or uncorrected QT>600 msec
- Bundle branch block: QTc(F)>530 msec (**Note:** QTc(F)>500 msec for Korean subjects)
- Change from baseline: QTc > 60msec

[Based on average QTc(F) value of triplicate ECGs. If an ECG demonstrates a prolonged QT interval, obtain 2 more ECGs over a brief period, and then use the averaged QTc(F) values of the 3 ECGs to determine whether the patients should be discontinued from the study].

Subjects are free to discontinue participation in the study at anytime. Every effort should be made to have the subject return for a Follow-up visit 4 weeks post last mepolizumab injection. In those instances where the subject specifies the reason for withdrawal of consent, this information will be captured in the eCRF.

A subject should only be designated as lost to follow-up if the site is unable to establish contact with the subject after 3 documented attempts via 2 different methods (phone, text, e-mail, certified letter, etc). These efforts should be documented in the clinic notes at the site.

Subjects may also be withdrawn from this study if mepolizumab becomes commercially available in the respective country, marketing of mepolizumab is no longer being sought in the respective country, or upon decision of the sponsor to discontinue further development of mepolizumab.

The primary reason for withdrawal will be recorded in the eCRF and any data collected up until the point of withdrawal will be used in the data analyses.

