- Withdraw the subject from the study after completion of the liver chemistry monitoring (unless further safety follow up is required)
- Do not re-challenge with investigational product.

In addition, for criterion 1:

- Make every reasonable attempt to have subjects return to clinic **within 24 hours** for repeat liver chemistries, liver event follow up assessments (see below), and close monitoring
- A specialist or hepatology consultation is recommended
- Monitor subjects twice weekly until liver chemistries (ALT, AST, alkaline phosphatase, bilirubin) resolve, stabilize or return to within baseline values

For criteria 2, 3, 4 and 5:

- Make every reasonable attempt to have subjects return to clinic **within 24-72 hrs** for repeat liver chemistries and liver event follow up assessments (see below)
- Monitor subjects weekly until liver chemistries (ALT, AST, alkaline phosphatase, bilirubin) resolve, stabilize or return to within baseline values; criterion 5 subjects should be monitored as frequently as possible.

Subjects with ALT \geq 5xULN and <8xULN which exhibit a decrease to ALT \geq 3xULN, but <5xULN and bilirubin <2xULN without hepatitis symptoms or rash, and who can be monitored weekly for 4 weeks:

- Notify the GSK medical monitor within 24 hours of learning of the abnormality to discuss subject safety

- Can continue investigational product
- Must return weekly for repeat liver chemistries (ALT, AST, alkaline phosphatase, bilirubin) until they resolve, stabilize or return to within baseline
- If at any time these subjects meet the liver chemistry stopping criteria, proceed as described above
- If, after 4 weeks of monitoring, ALT <3xULN and bilirubin <2xULN, monitor subjects twice monthly until liver chemistries normalize or return to within baseline values.

For criteria 1-5, make every attempt to carry out the **liver event follow up assessments** described below:

- Viral hepatitis serology including:
 - Hepatitis A IgM antibody;
 - Hepatitis B surface antigen and Hepatitis B Core Antibody (IgM);
 - Hepatitis C RNA;
 - Cytomegalovirus IgM antibody;
 - Epstein-Barr viral capsid antigen IgM antibody (or if unavailable, obtain heterophile antibody or monospot testing);
 - Hepatitis E IgM antibody

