### 9.3.2. On-Treatment Phase

The on-treatment phase for any purpose except the classification of exacerbations is defined as being from the day of the first administration to the day of the last administration of study treatment + another 28 days inclusive (but no greater than the data collection cut-off date).

i.e. time on-treatment will otherwise be defined as follows:

For all subjects:

(Date of last administration) – (Date of first administration) + 29  
but no greater than the data collection cut-off date.

This on-treatment phase will be divided into two periods partitioned at the date and time of receiving the new drug product. This transition will occur when a subject switches from dosing with MDP1 to be dosed with MDP2 for the remainder of the study.

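### SAP 9.3.1: follow-up time for the exacerbation-rate model is not capped at last dose + 28 days but the event window is, so read literally the annualised rate is expected to be slightly understated

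*SAP*

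**What the plan says.** SAP 9.3.1 opens with "In order to model the annualised rate of exacerbations, the reporting period for exacerbations will be as follows" and then prints two formulas. Subjects still in the study run from Visit 2 to the cut-off date, plus one day. Early withdrawals get "Date of withdrawal) – (Visit 2 date) + 1". Neither formula contains the date of the last dose.

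The closing sentence of 9.3.1 defines a differently named quantity, the on-treatment collection period. It runs from Visit 2 to the cut-off "or the date of withdrawal inclusive (but no greater than 4 weeks post last study dose received"). SAP 9.2.2 repeats the limit: "but no greater than 4 weeks post last study dose received), See Section 9.3.1". SAP 11.1 summarises the exacerbations that fall in the on-treatment phase, citing 9.3.1, and estimates the rate with a negative binomial model.

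The offset is named in SAP 8.2: "time on-treatment (as an offset variable) will also be included when estimating the annualised rate of exacerbations". No section is cited for its definition. SAP 9.3.2 has a time on-treatment formula with the 28 days built in, but introduces it with a carve-out: "The on-treatment phase for any purpose except the classification of exacerbations is defined as being from the day of the first administration".

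**The concern.** A rate needs its numerator and denominator to cover the same period. Here the limit at 4 weeks after the last dose is written for the events and not for the time formulas. Days beyond that limit enter the denominator although an exacerbation on those days cannot enter the numerator.

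The protocol leaves room for such days:

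- **Late follow-up visit.** Protocol 4.5 says "Every effort should be made to have the subject return for a Follow-up visit 4 weeks post last mepolizumab injection". The footnotes to Tables 2 and 3 allow ± 1 week, so the visit can fall 35 days after the last dose. If withdrawal is dated at that visit, the gap is 7 days.
- **Liver stopping criteria.** Drug stops at once, but Protocol 6.3.2 then says "Withdraw the subject from the study after completion of the liver chemistry monitoring (unless further safety follow up is required"). Monitoring can outlast 28 days.
- **Late or missed doses before a cut-off**, for subjects still in the study.

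Neither document defines the date of withdrawal. By Protocol 9.5, every subject has left the study at the final analysis. Protocol 4.5 describes leaving because of commercial availability as withdrawal, so the withdrawal formula could apply to nearly everyone.

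At stake are the reproducibility of a listed secondary endpoint, reported with a 95% confidence interval, and a small shift in its value.

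**Working it through.** The plan gives no rate, follow-up length or withdrawal pattern for this endpoint, so it has no figure to reproduce. Shares affected, gaps and follow-up times below are assumptions.

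**One subject, three candidate denominators.** Take Visit 2 as day 0 and the last dose at week 48 (day 336).

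- Printed 9.3.1 formula: withdrawal day − 0 + 1
- Capped 9.3.1 collection period: min(withdrawal day, 336 + 28) − 0 + 1
- 9.3.2 formula: 336 − 0 + 29

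| Withdrawal after last dose | Printed 9.3.1 | Capped period | 9.3.2 |
|---|---|---|---|
| 10 days | 347 | 347 | 365 |
| 28 days | 365 | 365 | 365 |
| 35 days | 372 | 365 | 365 |

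Events are counted in the capped period, and only that column matches the event window in every row. At 35 days the printed formula gives 365/372 = 0.981 of the matched rate, or 1.9% too low for that subject.

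**Direction.** The printed time is never shorter than the capped time. Events divided by person-time can therefore only be unchanged or too low.

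**Size, events over person-time.** Let p be the share affected, g the gap in days beyond last dose + 28, and L and S the follow-up in years of affected and other subjects:

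understatement = p·g / [(p·L + (1 − p)·S) × 365.25 + p·g]

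With g = 7:

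- p = 0.2, L = 1, S = 3: 1.4 / (949.65 + 1.4) = 0.15%
- p = 0.3, L = 1, S = 3: 2.1 / (876.6 + 2.1) = 0.24%
- p = 0.2, L = 0.5, S = 1: 1.4 / (328.73 + 1.4) = 0.42%
- p = 0.3, L = 0.5, S = 1: 2.1 / (310.46 + 2.1) = 0.67%
- all subjects, 1 year: 7 / (365.25 + 7) = 1.88%
- all subjects, 2 years: 7 / (730.5 + 7) = 0.95%
- all subjects, 3 years: 7 / (1095.75 + 7) = 0.63%

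**An extreme case.** SAP Section 3 still places post-treatment labs at 12 weeks, which the current protocol has replaced with 4 weeks. If withdrawal were dated at 12 weeks, g = 84 − 28 = 56:

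- p = 0.2, L = 1, S = 3: 11.2 / (949.65 + 11.2) = 1.17%
- p = 0.3, L = 0.5, S = 1: 16.8 / (310.46 + 16.8) = 5.13%

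**Check in the model class.** Intercept-only negative binomial fits to simulated data (N = 350, follow-up varied ± 30%, rates 0.3, 0.7 and 1.5 per year, dispersion 0.7 to 1.2, 150 data sets per scenario) compared the uncapped with the capped offset. Mean understatement:

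- 7 days, p = 0.2, L = 1, S = 3: 0.22-0.28%
- 7 days, p = 0.3, L = 0.5, S = 1: 0.75-0.85%
- 7 days, all subjects: 1.89-1.91% at 1 year, 0.65% at 3 years
- 56 days, p = 0.2 or 0.3: 1.67-5.98%

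Every fit moved down. A separate set (N = 400, rate 0.7, dispersion 0.8, wider spread of follow-up) gave 2.0% and 0.8% for 7 days in all subjects at mean follow-up of 1 and 3 years. The direction is guaranteed only for events over person-time; for the fitted model it is what to expect. These fits omit the SAP's covariates.

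**The case against.** **One definition, stated twice.** The closing sentence of 9.3.1 has the same start and the same two end points as the formulas, and its inclusive end date corresponds to the +1. It can be read as the full statement of one interval, cap included. The period that 9.3.1 calls on-treatment is the capped one, which fits the offset's name in 8.2. This reading is plausible and may be what was intended. It is not what the formulas print. In 9.3.2 and its subsections the last-dose limit for the final dosing period is built into the formula itself; in 9.3.1 it is not.

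**Both could be uncapped.** The reporting period might govern events as well as time, and then the two would match. But 9.2.2 and 9.3.1 cap the collection of exacerbations generally, and 11.1 relies on 9.3.1 for the events.

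**The gap may be rare or short.** This stands in part. SAP 12.8 mentions early withdrawal visits, so withdrawal may be dated before the follow-up visit. Even if every subject were dated at follow-up, visits spread evenly over ± 1 week would average 7/4 = 1.75 days past day 28: 1.75 / (365.25 + 1.75) = 0.48% at 1 year and 1.75 / (1095.75 + 1.75) = 0.16% at 3 years. Seven days in everyone is an upper edge, and the 56-day case rests on a superseded lab timing. Still, the cap would serve no purpose if dates could never fall beyond it.

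**Commercial availability may not count as early withdrawal.** Those subjects' time would then end at the cut-off date, which could widen the mismatch.

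**Sampling error is far larger.** This stands. With N = 350 and mean follow-up of 2.6 years, SE of the log rate ≈ √[(1/μ + k)/N], where μ is expected events per subject and k the dispersion. At 0.3 per year, μ = 0.78 and k = 1.2, giving 1.96 × SE = 0.17. At 1.5 per year, μ = 3.9 and k = 0.7, giving 0.10. The corresponding shift is 0.22-0.28%.

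**Conclusion.** The concern holds as a minor inconsistency. As printed, the time formulas and the event window do not cover the same period, and 8.2 does not settle which one the offset uses. Under the current 4-week follow-up visit and mean follow-up of at least 1 year, the expected understatement is about 2% at most and more likely a fraction of a percent. It reaches several percent only if many withdrawals are dated near 12 weeks. It is nil if every withdrawal date, and every cut-off date for subjects still in the study, falls within 28 days of the last dose.

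The size rests on assumed gaps, shares and follow-up times. No hypothesis test depends on the endpoint, and the primary safety endpoint is not affected.

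**What to change.** - **SAP 9.3.1:** replace the two formulas with one for every subject, whatever the reason for leaving: min(cut-off date, date of withdrawal, last dose + 28 days) − Visit 2 date + 1. State that exacerbations are counted in that same window. For subjects still in the study the withdrawal term drops out.
- **SAP 9.3.1:** define the date of withdrawal, and say which subjects who leave because of commercial availability or study closure it covers.
- **SAP 8.2:** name the offset as the natural log of this time and cite 9.3.1.

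The cost is one formula, one definition and one phrase. No new data are needed. If the cap was always meant for both quantities, the edit only records it.

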### 9.3.2. On-Treatment Phase

The on-treatment phase for any purpose except the classification of exacerbations is defined as being from the day of the first administration to the day of the last administration of study treatment + another 28 days inclusive (but no greater than the data collection cut-off date).

i.e. time on-treatment will otherwise be defined as follows:

For all subjects:

(Date of last administration) – (Date of first administration) + 29  
but no greater than the data collection cut-off date.

This on-treatment phase will be divided into two periods partitioned at the date and time of receiving the new drug product. This transition will occur when a subject switches from dosing with MDP1 to be dosed with MDP2 for the remainder of the study.

#### 9.3.2.1. Mepolizumab Drug Product 1 Period

For those subjects that have transitioned onto MDP2, the mepolizumab drug product 1 period starts on the first day of dosing with MDP1, and ends the minute prior to the first dose of MDP2.

For those subjects that have not transitioned onto MDP2, the mepolizumab drug product 1 period is defined as being from the day of the first administration using MDP1 to the day of the last administration using MDP1 + another 28 days inclusive (but no greater than the data collection cut-off date).

i.e. time within the mepolizumab drug product 1 period will be defined as:

(Date of first MDP2 administration) – (Date of first MDP1 administration) + 1  
for those subjects that have transitioned onto MDP2 **or**

(Date of last MDP1 administration) – (Date of first MDP1 administration) + 29  
(but no greater than the data collection cut-off date) for those subjects that have not transitioned onto MDP2.

